## 1.5 OVERALL SYNOPSIS OF THE CLINICAL INVESTIGATION

Clinical investigation single identification #:	Clinicaltrials.gov #NCT06085443
Clinical investigation plan #:	23E1670
Title of the clinical investigation:	CLINICAL STUDY TO EVALUATE THE SAFETY AND EFFECTIVENESS OF A AURICULAR SPRAY MEDICAL DEVICE "EAR HYGIENE"
Sponsor:	YSLAB [name] [name] [name] FRANCE
Development phase:	Post market study Device used according to IFU
Objectives:	
Principal aim: SAFETY
 
The primary objective of the study is to confirm the safety of a marketed auricular spray with reverse and microdiffusion nozzle by clinical examination by ENT specialist and by the scoring of the irritation of the ear canal at D60 in comparison with basal scoring of irritation at D0 (scale 0 to 3) such as:
 
 
- 0: no irritation,
 
- 1: slight irritation (located slight erythema and/or dryness),
 
- 2: moderate irritation (clear erythema or dryness which may be visible on the whole treated area),
 
- 3: severe irritation (serious erythema with potential oedema and/or scar).
 
 
Potential adverse events collection.
 
Secondary aims: EFFICACY/PERFORMANCE PREVENTION for investigational device with reverse nozzle, investigational device with microdiffusion nozzle and for control group, in comparison to the baseline (D0) and between groups:
 
 
• scoring of the obstruction of ear canal by the Investigator
 
 
0: no obstruction – normal and/or no significant presence of cerumen in the ear canal. The membrane is clearly visible.
 
1: <25% minimal, very little and mostly insignificant impacted cerumen. The tympanic membrane is visible, but with still a little bit cerumen.
 
2: 25-50% mild, some excessive impacted cerumen causing partial occlusion of the ear canal. The tympanic membrane is not entirely visible, quite difficult to see.
 
3: 50-75% moderate, moderate and excessive impacted cerumen causing partial occlusion of the ear canal. Partial to very little of the tympanic membrane is visible.
 
4: 75-100% severe, severe and excessive impacted cerumen causing partial or complete occlusion of the ear canal. Little if any of the tympanic membrane is visible.
 
 
• audiogram with classification of the loss or gain hearing function using the following scale (only for subjects more than 6):
 

YSLAB	Medical Device CIP #23E1670	Final version 2.0 Date: 09/11/2023	Confidential Page 11/64
-------	--------------------------------	---------------------------------------	----------------------------

	
No hearing function loss, hearing function loss between 5 to 10dB, hearing function >10dB (Subha et al.2006), hearing function win between 5 to 10 dB, hearing function win >10dB.
 
Additionally, the secondary objective of this study will be to see if the investigational device is more efficient in children, adults or elderly subjects (for both nozzles - reverse or microdiffusion).
 
 
• Subject's self-evaluation using a questionnaire.
 
• Evaluation of the effect on the number of auricular affection (such as otitis) during the use period (daily log).
 

Design:	Open study, randomized, before / after treatment, with tested product versus control group, in parallel groups
Planned Sample Size:	
99 included subjects and results delivered on 90 subjects.
 
 
• 1 group of 72 included subjects in order to have results on 66 subjects (33 subjects using product with the "reverse diffuser" and 33 using the product with the "microdiffusion diffuser")
 
• 1 group of 27 included subjects in order to have results on 24 subjects not using a spray (control group). (in case of discomfort or pain, they are allowed to use ear drops prescribed by a doctor after a medical examination)
 

Number of investigational study sites:	2 centers
Inclusion criteria:	
 
1. Gender: female and/or male.
 
2. Age: 
 
- 30 to 40% having age between 3 to 12 yo,
 
- 30 to 40% between 13 to 65 yo,
 
- 30 to 40% more than 65 yo.
 
 
 
3. Subjects able to use the tested product.
 
4. Subjects having history of cerumen occlusion more than once a year with or without symptoms (reduction of hearing function, obstruction feeling of the ear canal,..).
 
5. Subjects having ear help system or regular users of systems such as anti-noise plugs or headsets (only for the 13yo subjects and more).
 
6. Subjects having a clinical score of ear canal obstruction of 2 or 3 at D0.
 

Exclusion criteria:	
 
1. Subjects who had surgical act on the mastoïde.
 
2. Subjects who had severe troubles of the internal ear (severe dizziness, desorientation, nausea).
 
3. Subjects using regularly a ear spray for washing his/her ears.
 
4. Subjects having a score of ear canal obstruction at 4 at D0.
 
5. Pregnant or nursing woman or planning a pregnancy during the study;
 
6. Subject who had been deprived of their freedom by administrative or legal decision or who is under guardianship;
 
7. Subject in a social or sanitary establishment;
 
8. Subject suspected to be non-compliant according to the investigator's judgment;
 
9. Subject with a condition or receiving a medication which, in the investigator's judgment, put the subject at undue risk;
 
10. Subject suffering from a severe or progressive disease.
 

Investigational device: Name / code	
OCEAN BIO-ACTIF Ear Hygiene (reverse nozzle)
 
OCEAN BIO-ACTIF Ear Hygiene (microdiffusion nozzle)
 
Bag on valve spray, with ergonomic nozzle

YSLAB	Medical Device CIP #23E1670	Final version 2.0 Date: 09/11/2023	Confidential Page 12/64
-------	--------------------------------	---------------------------------------	----------------------------

Galenic form	2 sprays in ear, every 3 days at home
Dosage	90 days
Duration	Topical to ear canal
Administration route	
Endpoints:	
Primary endpoints:
 
 
• Clinical evaluation,
 
• Clinical score of the irritation with structured scale,
 
• Record of the possible adverse reactions.
 
 
Secondary endpoints:
 
 
• Clinical score of the obstruction of ear canal,
 
• Results of audiogram with classification of the loss or win hearing function
 
• Subject satisfaction survey
 
• The number of auricular affection (such as otitis) during the use period
 

Study Procedures:	D0, D90
Statistical methods:	
The analysis of the primary endpoint will be performed on the ITT and population.
 
The analysis of the secondary endpoint will be performed on the population.
 
The analysis of the safety/tolerance parameters will be performed on "safety" population.
 
Primary endpoint:
 
The irritation is assessed by the Laryngologist using a 4-point structured scale (from "No irritation (0)" to "Severe irritation (3)" on D0 and D90).
 
For each product, a paired t-test will be used to test whether the change from baseline (D90-D0) differ significantly from 0. The normality assumption will be checked using a Shapiro-Wilk test (<math>\alpha=0.01</math>), in case of rejection, a Wilcoxon signed ranks test will be used.
 
To test whether the products differ statistically in terms of change from baseline (D90-D0), a two-sided t-test is used. If the normality assumption is not met, a non-parametric approach is used with a Wilcoxon signed rank test.
 
Secondary endpoints:
 
For each secondary parameter:
 
 
• Clinical score of the irritation with structured scale
 
• Clinical score of the obstruction of ear canal
 
• Results of audiogram with classification of the loss or win hearing function.
 
• The number of auricular affection (such as otitis) during the use period
 
 
For each product, a paired t-test will be used to test whether the change from baseline (D90-D0) differ significantly from 0. The normality assumption will be checked using a Shapiro-Wilk test

YSLAB	Medical Device CIP #23E1670	Final version 2.0 Date: 09/11/2023	Confidential Page 13/64
-------	--------------------------------	---------------------------------------	----------------------------

	
(<math>\alpha=0.01</math>), in case of rejection, a Wilcoxon signed ranks test will be used.
 
To test whether the products differ statistically in terms of change from baseline (D90-D0), a two-sided t-test is used. If the normality assumption is not met, a non-parametric approach is used with a Wilcoxon signed rank test.
 
For the subjective evaluation questionnaire:
 
For each item of the subjective questionnaire, the raw data will be summarized in frequency (N) and percentage (%) by group of product.
 
All statistical tests will be assessed at <math>\alpha = 5\%</math> level of significance in a bilateral approach.
 
Statistical software: SAS® v9.4.

Foreseen study duration:	
Clinical investigation beginning: Q4 2023
 
Clinical investigation end: Q3 2024
 
Clinical investigation global duration: 8 months
 
Duration by subject: 90 days

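### The audiogram endpoint is a class of hearing change, yet the plan tests its D90 minus D0 difference; the test belongs on the dB values, and the classes need exclusive definitions

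*Combined protocol and SAP*

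**What the plan says.** All references are to section 1.5 (overall synopsis) and the flow chart.

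- **Objectives, secondary aims.** Comparisons against baseline and between groups include "audiogram with classification of the loss or gain hearing function using the following scale (only for subjects more than 6". The scale opens "No hearing function loss, hearing function loss between 5 to 10dB, hearing function", where the last item is followed only by a figure above 10 dB. It ends "hearing function win between 5 to 10 dB, hearing function win", where the last item is again above 10 dB.
- **Endpoints.** The secondary endpoint is "Results of audiogram with classification of the loss or win hearing function".
- **Statistical methods, secondary endpoints.** The same classified result is on the list of secondary parameters. For each of these, within product, "a paired t-test will be used to test whether the change from baseline (D90-D0) differ significantly from 0". A Wilcoxon signed-rank test replaces it if a Shapiro-Wilk test rejects normality.
- **Between products.** "To test whether the products differ statistically in terms of change from baseline (D90-D0"), a two-sided t-test is planned, with a non-parametric fallback.
- **Flow chart.** The audiogram is marked at both D0 and D90.

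**The concern.** The irritation score (0 to 3) and the obstruction score (0 to 4) describe a state. Each can be given at D0 and again at D90, and the two can be subtracted. The audiogram classes describe movement between two audiograms, so there is nothing to subtract at D0. The plan nevertheless treats all these parameters alike.

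The class boundaries add a second problem. Gains are where a hearing benefit would appear in subjects who enter with an obstruction score of 2 or 3. On a literal reading, gains are also the values that satisfy more than one class.

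The audiogram is the only instrumented hearing measure among the endpoints. If the text stays as it is, someone must decide after the data are in what is tested and where the class limits lie. The study is open, so that decision could be made knowing the results.

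**Working it through.** The plan gives no sample-size, power or alpha figure for this endpoint, so there is none to reproduce. The check has two parts.

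**1. Can D90 minus D0 be formed on the class?**

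- Let A0 and A90 be a subject's audiogram values in dB at D0 and D90, and let c be the change between them, signed so that a gain is positive and a loss negative.
- The class is a function of c, so it needs both A0 and A90. It exists once per subject, at D90.
- The class at D90 minus the class at D0 needs a class at D0, when only A0 exists. The difference is therefore not defined.
- Reading the loss classes as absolute hearing level at one visit does not help, because a win cannot exist at a first visit.
- The dB difference between A0 and A90 is defined for every subject with both audiograms, and the flow chart schedules both.

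**2. Does each change fall in exactly one class?**

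The classes are taken literally, with the third read as a loss above 10 dB: no loss, c ≥ 0; loss 5 to 10, -10 ≤ c ≤ -5; loss above 10, c < -10; win 5 to 10, 5 ≤ c ≤ 10; win above 10, c > 10.

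| c (dB) | Classes met |
|---|---|
| -12 | loss above 10 |
| -10, -5 | loss 5 to 10 |
| -3, -1.25 | none |
| 0, +3 | no loss |
| +5, +8, +10 | no loss and win 5 to 10 |
| +12 | no loss and win above 10 |

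Counts over the range -20 to +20 dB:

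- **5 dB steps (9 values):** 0 meet no class, 5 meet one and 4 meet two (+5, +10, +15, +20).
- **1.25 dB steps (33 values; assumed, as for a mean of four frequencies each read in 5 dB steps):** 3 meet no class (-1.25, -2.5, -3.75), 17 meet one and 13 meet two (+5 to +20).
- **Third class left without a direction:** a gain above 10 dB meets three classes (2 of 9 values, or 8 of 33).
- **No-loss class read as a change under 5 dB either way, third class read as a loss:** every value meets exactly one class (9 of 9 and 33 of 33).

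These are counts of possible values, not of subjects. To give a rough idea of subjects, assume c is normal with mean m from -2 to +5 dB and SD s of 5 or 8 dB. None of these figures is in the documents.

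- Share with no class = Φ((0 - m)/s) - Φ((-5 - m)/s). For m = -2, s = 5: Φ(0.4) - Φ(-0.6) = 0.381. For m = 5, s = 5: Φ(-1) - Φ(-2) = 0.136.
- Share with two classes = 1 - Φ((5 - m)/s). For m = -2, s = 5: 1 - Φ(1.4) = 0.081. For m = 5: 0.500.

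Over that range, about 14% to 38% would have no class and 8% to 50% would have two, on the literal reading with finely recorded changes.

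**The case against.** The best defence is that the endpoint wording can mean the audiogram result together with a classification. On that reading, the dB values at D0 and D90 are what is tested and the class is only a summary. The flow chart makes this feasible. It is also true that a paired test is a one-sample test on a change, so classes given signed codes around no change could be tested directly. What stands is that a reader should not infer that hearing cannot be tested in this trial. What does not stand is that the plan already says how: the synopsis neither states that dB is tested nor gives signed codes, and both the endpoint and the analysis list name the classified result.

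Second, two win classes sit beside the no-loss class, so its natural meaning may be no relevant change. Overlap and gap then both vanish. This is a fair reading, but the synopsis does not state it, and it does not supply a class at D0. The missing direction word is very probably a slip for loss.

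Third, the gap for small losses needs changes finer than 5 dB, and the synopsis gives no measurement step or averaging rule. With single thresholds in 5 dB steps there is no gap, although the literal overlap remains.

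Two stronger inferences are tempting and unsupported. A reader might suppose that the classes will be scored in listed order and averaged, so that losses and wins run in the same direction. The synopsis numbers the irritation and obstruction scales but not the audiogram classes, so no such scoring is planned. A reader might also suppose that the two centres will file gainers differently. Nothing says who assigns the class, or that practice would differ.

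**Conclusion.** The point holds in this form: D90 minus D0 cannot be formed on the class that the plan names, though it can be formed on the dB values from the two scheduled audiograms. This does not depend on how the classes are read.

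The overlap depends on reading the no-loss class literally, in which case it covers every gain of 5 dB or more. The gap needs that reading too, and also changes recorded more finely than 5 dB; it then covers losses above 0 and below 5 dB.

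The endpoint is secondary and limited by age, and the primary irritation analysis is unaffected. The text should be corrected before analysis; the point is no threat to the trial's main conclusion. Only the synopsis and flow chart were available (the synopsis footers show pages 11 to 13 of 64), so a fuller definition in the body of the plan could not be checked. The study cited for the scale was not available either.

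**What to change.** - **Test dB.** Make the tested hearing variable the D90 minus D0 difference in dB, using one prespecified average over a fixed set of frequencies and the same ear at both visits. These details are needed because the synopsis has no averaging or ear rule. Apply the planned within-group and between-group tests to it. The between-group rank fallback must be a two-sample test; the synopsis names a signed-rank test there, which is a separate matter.
- **Take the class off the tested list.** Remove it from the parameters tested as D90 minus D0.
- **Redefine the classes for description only,** as five exclusive ordered categories: loss above 10 dB; loss of 5 to 10 dB; change under 5 dB in either direction; gain of 5 to 10 dB; gain above 10 dB.

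The cost is protocol and analysis-plan wording, plus recoding any class already recorded from its dB values. No visit or procedure is added.

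### The synopsis does not tie the age quotas to the randomised arms, and it names neither age stratification nor an age term, so age mix can differ between arms by chance

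*Combined protocol and SAP*

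**What the plan says.** All references are to section 1.5, the overall synopsis.

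- **Inclusion criteria (age).** There are three quotas: "30 to 40% having age between 3 to 12 yo", "30 to 40% between 13 to 65 yo" and "30 to 40% more than 65 yo". None states whether the percentage applies to the whole sample or to each arm.
- **Design.** "Open study, randomized, before / after treatment, with tested product versus control group, in parallel groups". No stratification factor is named.
- **Planned sample size.** "99 included subjects and results delivered on 90 subjects". For the sprays, "1 group of 72 included subjects in order to have results on 66 subjects", of whom 33 use each nozzle. The control group has 27 included and 24 with results.
- **Objectives.** Performance is assessed for each nozzle and for control, against D0 and between groups. A further secondary objective is to "see if the investigational device is more efficient in children, adults or elderly subjects", for both nozzles.
- **Statistical methods.** Between-product differences in D90-D0 change are tested with no age term. No test is named for the age objective.

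**The concern.** The plan treats age as a possible modifier of the effect, since it asks whether performance differs by age band. Age also carries a second difference: the criterion on hearing aids, ear plugs or headsets applies only from 13 years.

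Quotas met over the whole sample do not make the bands equal across arms, and the control arm is small. If allocation ignores age, part of an observed spray-control difference may reflect a different age mix, and the planned tests do nothing to remove it. Some age-by-arm cells may also be too small to describe. The child cells shrink further for the audiogram, which the Objectives limit to subjects older than 6.

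**Working it through.** The plan states no imbalance probability, so there is no figure to reproduce. Its counts do add up: 72 + 27 = 99 included and 66 + 24 = 90 with results.

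**Inputs.** From the documents: 99 included, 72 spray, 27 control, and quotas of 30% to 40% per band. Assumed: 33 per band (99/3), spray split 36/36 at inclusion (72/2), simple random allocation to fixed arm sizes, and dropout unrelated to age.

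**Step 1: what a 20-point gap means, pooled spray against control.** With c control subjects in a band, spray has 33 - c, so

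gap = c/27 - (33 - c)/72 = (c - 9) × (1/27 + 1/72) = (c - 9) × 0.0509.

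A gap of 0.20 needs |c - 9| ≥ 0.20/0.0509 = 3.93, that is, 5 or fewer or 13 or more control subjects where 9 are expected.

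**Step 2: probability for one band.** c is hypergeometric (27 drawn from 99, of whom 33 are in the band). P(c ≤ 5) = 0.044 and P(c ≥ 13) = 0.048, total 0.092.

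**Step 3: at least one of three bands.** Exact enumeration of the multivariate hypergeometric gives 0.211. Over every whole-number mix that meets the quotas, the result runs from 0.131 (30/31/38) to 0.211 (33/33/33). For a single given band the range is 0.050 to 0.092.

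**Step 4: nozzle arms separately.** From 200,000 simulated allocations, any band, gap of at least 20 points:

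| Comparison | 36/36/27, 33 per band | 33/33/24, 30 per band |
|---|---|---|
| Pooled spray vs control | 21% | 18% |
| One given nozzle vs control | 22% | 26% |
| Either nozzle vs control | 34% | 42% |

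**Step 5: cell sizes.** With 33 per band at inclusion, the 95% ranges per band are 5 to 13 for control, 8 to 16 for each nozzle and 20 to 28 for pooled spray.

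**Step 6: size of a shift, illustration only.** The documents give no SD and no difference between bands. Assume SD 1 and a difference in change of 0.5 to 1 grade between one band and the others. A 20-point gap then moves the arm difference by 0.20 × 0.5 = 0.1 to 0.20 × 1 = 0.2 grade. For 33 against 24 subjects, SE = √(1/33 + 1/24) = 0.268, so the shift is 0.1/0.268 = 0.37 to 0.2/0.268 = 0.75 SE, given that such a gap has occurred.

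**Step 7: if the quotas held within each arm.** In a control arm of 27, 30% to 40% is 8.1 to 10.8, so each band has 9 or 10, and a total of 27 forces 9/9/9. Spray would have 22 to 28 per band. The largest gap is 28/72 - 9/27 = 0.389 - 0.333, or 5.6 points. With 33 per band and exact stratification it is zero. Unstratified allocation gives 9/9/9 in control only about 4% of the time.

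**The case against.** **The quotas may already apply within arms.** The supplied text is a synopsis and flow-chart, with footers showing pages 11 to 13 of 64 and no randomisation section. The arm sizes also divide into exact thirds: 27 into 9, 72 into 24, 33 into 11, 24 into 8. This stands as a limit. A reader might infer that the plan sets quotas only over the whole sample and does not stratify. The documents support only that the synopsis does not say.

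**Chance imbalance is not bias.** This stands. Under randomisation, the standard error and type I error of the unadjusted test already allow for it. What is lost is precision: if one third of subjects differ by d grades from the rest, age accounts for (1/3)(2/3)d² = 2d²/9 of the variance, or 6% to 22% of a total SD of 1 for d = 0.5 to 1. An age term in the analysis would recover much of that without changing allocation, but it would not refill a control cell of 5.

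**One in three is not the spray-control figure.** This stands. A reader might take 34% as the chance that spray and control differ in age mix. It counts either of two nozzle arms and any of three bands. For pooled spray the figure is 13% to 21%.

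**The age objective concerns device users.** This largely stands. About 20 to 28 spray users per band remain whatever happens in control, so a comparison of bands among users is not confounded by spray-control imbalance. Even perfect stratification leaves only 9 control subjects per band, about 8 with results.

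**The primary aim is untouched.** This stands for the within-product comparison of irritation with D0, which the arms' age mix does not enter.

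**Conclusion.** The point holds as a modest, avoidable weakness. On the synopsis alone, nothing keeps age balanced between arms and nothing in the between-group tests accounts for it. The chance of a 20-point gap in at least one band is about 21% for pooled spray against control and about 34% for one or other nozzle arm against control. These figures rest on unstratified allocation, a 36/36 split and 33 per band; other permitted quota mixes lower the pooled figure to as little as 13%.

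The consequence is less precise and less readable secondary between-group comparisons, and small, uneven age-by-arm cells. A reader might go further and infer biased tests, an undermined primary safety conclusion or an invalid age objective. The documents support none of these, for the reasons given under the objection. If the full protocol already stratifies by age band, the allocation part of the point is met and only the missing age term remains.

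**What to change.** 1. Stratify the randomisation by the three age bands, or cite the section of the full protocol that already does so, and state that the quotas apply within each arm.
2. Allocate 4:4:3 within each band, since 36:36:27 reduces to 4:4:3. With 33 in a band, three blocks of 11 give 12/12/9. The quotas also allow other band totals (30 to 39 of 99), for which the last block would be incomplete.
3. Use a central list and keep block sizes undisclosed, because the study is open.
4. Include age band as a stratum or covariate in the between-group analyses.

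**Cost.** Three lists in place of one, and no extra subjects; meeting the quotas already requires recruitment to be tracked by age band. The downsides are small: incomplete last blocks, more so if each of the 2 centres holds its own lists (six strata averaging 99/6 = 16.5 subjects), and slightly more predictable allocation near the end of a block.

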## FLOW-CHART

Procedure (time-points)	V1	V2
Intervals	D0	D90 (+/-3)
Informed Consent	●	
Medical exam	●	
Medical background and previous treatment	●	
Clinical scoring including irritation of the ear canal	●	●
Audiogram	●	●
Dispense product and daily log	●	
Collect product and daily log		●
Subjective evaluation questionnaire		●
Adherence control, record of AE, concomitant treatments	●	●
End of study form		●

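### The ear-affection count is tied to a period of product use that is not defined for controls or early stoppers, and its planned D90-D0 test does not fit a count that starts at D0

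*Combined protocol and SAP*

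**What the plan says.** The Objectives row of section 1.5 sets the aim as "Evaluation of the effect on the number of auricular affection (such as otitis) during the use period (daily log"). The Endpoints row lists "The number of auricular affection (such as otitis) during the use period" as a secondary endpoint, and the Statistical methods row repeats the same use-based window. No row of the synopsis defines it.

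The secondary aims cover both nozzles and extend to results "for control group, in comparison to the baseline (D0) and between groups". The Planned Sample Size row describes the control group as "24 subjects not using a spray (control group").

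The flow-chart has two visits, D0 and D90 (+/-3). The log appears in two rows only: "Dispense product and daily log" at D0 and "Collect product and daily log" at D90. No row or footnote is specific to a group. A separate row, "Adherence control, record of AE, concomitant treatments", is marked at both visits. The study duration row gives "Duration by subject: 90 days".

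Under Statistical methods, this count is one of the secondary parameters to be analysed as change from baseline (D90-D0). Each product gets a paired t-test, or a Wilcoxon signed ranks test if normality is rejected. Products are compared on the same change by a two-sided t-test or a Wilcoxon test. Neither a rate nor follow-up time is mentioned.

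**The concern.** A count of episodes can be compared between groups only if every group is observed over the same kind of window and with the same recording tool. Here the window is worded by use of a product that one group does not use, and the tool is listed alongside that product. Two questions are left open: over what days, and from what source, are control episodes counted; and does a spray user who stops at, say, D45 go on being counted to D90?

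In an open study these choices should not be left until the data are in hand. With no visit between D0 and D90, the log is the only listed record kept in between. A control subject without one would be reporting 90 days of ear problems from memory.

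The analysis adds a second difficulty. The count begins at D0, so a D90-D0 difference has meaning only if a count over some period before D0 is also taken. None is described.

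**Working it through.** The plan gives no event rate, effect size or stopping rate for this endpoint, so it has no figure to reproduce. Its subject numbers are consistent: 72 + 27 = 99 included and 66 + 24 = 90 evaluable. The implied losses are 6/72 = 8.3% (spray) and 3/27 = 11.1% (control). These are losses of evaluable subjects, not stopping rates.

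**1. If counting ended at last use and controls were counted for 90 days.** Let a share s of spray users stop at times T spread evenly over 0-90 days. The mean share of the window lost is s × (1 − 45/90) = s/2.

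| Assumed s | Person-time lost | Spray count relative to full window |
|---|---|---|
| 8.3% | 4.2% | 0.96 |
| 20% | 10% | 0.90 |
| 30% | 15% | 0.85 |

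The 8.3% borrows the planned spray loss as a stand-in; the other shares are pure assumptions. If all stoppers stopped on a single day t, the ratio would be 1 − s × (1 − t/90). Over s from 8.3% to 30% and t from D30 to D60, this runs from 0.80 to 0.97.

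In events, with 66 evaluable spray users and the same true rate in all groups:
- Assumed 0.2 episodes per subject per 90 days: 66 × 0.2 = 13.2 expected over the full window, falling to 12.7 (s = 8.3%) or 11.2 (s = 30%).
- Assumed 0.05 episodes: 3.3 expected, falling to 3.2 or 2.8.

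**2. If spray users were counted to D90 but controls kept no log.** With 24 evaluable controls the expected control count is 24 × 0.2 = 4.8, or 24 × 0.05 = 1.2. Missing a single control episode would remove 1/4.8 = 21%, or 1/1.2 = 83%, of the expected control count. At the higher rate the apparent spray-to-control ratio would then be 4.8/3.8 = 1.26 with no true difference. This error runs against the spray.

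**3. If the window were D0-D90 for everyone, with the same log.** The window ratio is 1.00 and neither bias arises.

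**4. The planned test.** Counting starts at D0 and no look-back is described, so the D0 value is either missing or zero by construction. If it is set to zero, the change is simply the count. The paired test then asks whether the mean count differs from zero, and any episode at all pushes it above zero. That says nothing about whether the spray prevents episodes. Unequal follow-up, including from dropout, is not corrected in either the within-product or the between-product test.

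**The case against.** The strongest reply is that the period of use simply means the 90 days of the study. Duration is 90 days per subject, the log comes back at D90, and no rule ends counting at the last spray. The flow-chart is one generic chart for all groups. It does not say that controls go without a log, and naming the control group in the secondary aims suggests that their data are to be collected. An otitis after stopping can also be picked up as an adverse event, which is recorded at both visits with no restriction by group or by use. An affection that itself causes stopping would be counted in any case; only later ones could be lost.

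Most of this stands. A reader might infer that controls have no counting period, that users who stop also stop being counted, and that the spray is therefore favoured. The documents support none of these as fact. The last inference also needs controls to be counted for the full 90 days, which sits badly with the first, and a missing control log would act in the opposite direction.

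What remains is that the 90-day reading is nowhere stated for this endpoint. Planned use is 90 days but actual use can be shorter, and the flow-chart itself schedules an adherence check. Adverse event recording at two visits is only a partial substitute, because the Objectives row names the daily log as the source. The objection also leaves the missing D0 count untouched.

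Once the window is common to all groups, a follow-up offset matters little except for dropouts. That is fair, but it costs nothing. The text available is the synopsis and flow-chart, so a definition may exist elsewhere in the full plan.

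**Conclusion.** The definition gap is real and should be closed. In the synopsis and flow-chart, the counting window and the log are not specified for controls or for subjects who stop early, although a between-group comparison is intended. Counts may therefore not be comparable, and the direction of bias cannot be determined from the documents.

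The size is illustrative only. If counting ended at last use, the spray count would be understated by about 4% at an assumed 8.3% stopping and by 15% at an assumed 30%, with evenly spread stopping times and a constant, equal event rate. If controls kept no log, the error would go the other way and could be larger, because only about 1 to 5 control episodes are expected at the assumed rates.

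The mismatch between a D90-D0 change and a count that accrues after D0 needs no such assumptions; it follows from the text supplied. As this is a secondary endpoint, the point is one that should be fixed rather than one that undermines the trial.

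**What to change.** - **Endpoint:** count episodes with onset after D0 and up to the D90 visit, or last contact if earlier, in all three groups, whether or not the spray is still in use.
- **Flow-chart:** state that control subjects also receive the daily log at D0 and return it at D90, and that spray users who stop keep filling it in.
- **Analysis:** for this endpoint, replace the D90-D0 change with a between-group rate ratio, exact or Poisson, with follow-up time as offset.
- **Sensitivity:** report a count restricted to time on use, if wanted, only as a sensitivity result.

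The cost is one endpoint sentence, one flow-chart footnote, one model line, and continued log keeping by controls and by subjects who stop. No extra visits or subjects are needed.
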